6.5.3 Vital Signs

Vital signs (systolic blood pressure, diastolic blood pressure, and pulse rate) will be summarized using mean, standard deviation, minimum, maximum and median by treatment group and analysis visit. Additionally, a within-subject change will be calculated per analysis visit as the post-baseline measurement minus the baseline measurement and summarized by treatment group and visit.

6.5.4 Electrocardiograms

ECG variables will be summarized using mean, standard deviation, minimum, maximum and median for each treatment group at each analysis visit, including changes from baseline.

Number and percent of subjects with normal and abnormal results as assessed by the central reader for the 12 lead ECG will be tabulated by treatment group at each analysis visit.

The QTc interval will be summarized using frequency tables for each analysis visit for values of clinical importance using the range criteria below.

| | QTc Interval Criteria Value (msec) |
|------------------------|------------------------------------|
| Normal | ≤ 4 50 |
| Borderline | > 450 |
| Prolonged | > 480 |
| Clinically significant | > 500 |

Number and percent of subjects with 12 lead ECG abnormalities as well as number and percent of subjects whose 12 lead ECG reading changed from normal at baseline to abnormal will be tabulated by treatment group at each analysis visit.

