6 STATISTICAL METHODOLOGY

6.1 General Considerations

As a result of this study design and the re-randomization of subjects originally assigned to placebo, there are four treatment groups which will be described in the 52-week analysis:

• Subjects originally randomized to 30 mg: 30 mg => 30 mg; per protocol, these subjects will have up to 12 months of fezolinetant exposure.

- Subjects randomized to placebo who will be re-randomized to 30 mg: placebo => 30 mg; per protocol, these subjects will have up to 9 months of fezolinetant exposure.
- Subjects originally randomized to 45 mg: 45 mg => 45 mg; per protocol, these subjects will have up to 12 months of fezolinetant exposure.
- Subjects randomized to placebo who will be re-randomized to 45 mg: placebo => 45 mg; per protocol, these subjects will have up to 9 months of fezolinetant exposure.

Continuous data will be summarized descriptively including the number of subjects (n), mean, standard deviation (SD), median, minimum and maximum. Categorical data will be summarized by frequencies and percentages. Percentages by categories will be based on the number of subjects with no missing data, i.e., the percentages for the non-missing categories will add up to 100%.

All summaries are descriptive and there are no statistical comparisons within the 52-week analyses.

All data summarization and analyses will be performed using SAS® on Unix. Specifications for table, figures, and data listing formats can be found in the Tables Listings and Figures (TLF) specifications.

As mentioned in the introduction, this analysis plan describes the analyses of the entire 52-week study for subjects who received fezolinetant, excluding the 12-week double blind analyses which is planned in a separate SAP.

Listings will include baseline data and data from first dose of fezolinetant, unless otherwise noted.

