6.5.2.1 Liver Safety Assessment

The liver safety assessments will be summarized by the categories below based on the measurements from Alkaline Phosphatase (ALP), Alanine Transaminase (ALT), total bilirubin, Aspartate Transaminase (AST) and their combination. These parameters will be based on measurements from a central laboratory.

The subject's highest value during the entire active-dose study period (from day of first dose of fezolinetant until last dose of extension treatment period + 1 day) will be used.

- ALT > 3xULN, > 5xULN, > 8xULN, > 10xULN, > 20xULN
- AST > 3xULN, > 5xULN, > 8xULN, > 10xULN, > 20xULN
- ALT or AST > 3xULN, > 5xULN, > 8xULN, > 10xULN, > 20xULN
- ALP > 1.5 xULN
- Total Bilirubin > 2xULN
- (ALT or AST > 3xULN) and Total Bilirubin > 2xULN
- (ALT or AST > 3xULN) and ALP < 2xULN and Total Bilirubin > 2xULN

The last 2 criteria where 2 or more parameters are evaluated will be with the measurements on the same day or up to 1 day apart. The denominator for each criterion will be the number of subjects who have at least one value during the active-dose study period. The number and percentage of subjects meeting the criteria during the active-dose study period will be summarized by treatment group.

Due to the COVID-19 pandemic, subjects might not have been able to visit the clinical site and have clinical laboratory tests taken at the clinical site and evaluated by the central laboratory, in this case clinical laboratory tests were performed taken by a local laboratory. The liver biochemistry safety assessments will be summarized including central and locally collected laboratory data due to the COVID-19 pandemic. This analysis is considered the primary analysis for the liver safety assessment.

As a secondary analysis for liver biochemistry, the analysis will be repeated with the data evaluated by the central laboratory but excluding the data that are impacted by COVID-19 pandemic, which include the data recorded after the subjects were diagnosed of COVID-19, after study drug discontinuation due to COVID-19, during dose interruption due to COVID-19, and visits that are out of protocol windows or data collected via home visits due to COVID-19 recorded in the eCRF.

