6.10.1.2 Safety Analysis Windows

Except for adverse events, for the analysis window, the last day is always 1 day after the last day of exposure to overall study treatment.

The end of overall treatment is defined as the last day of treatment (e.g., discontinued study or entered follow-up period) +1 and the follow-up period for analysis windows begins at last overall treatment + 2 days and onward (Follow-up Study Day 2).

| Analysis | Scheduled | Analysis Windows (Fezolinetant day) | | | |
|-----------|--------------------|-------------------------------------|----------------------|---------------------|-----------------|
| Visits | Day in Protocol | a) | b) | c) | d) |
| Baseline | Day 1 | Last non-missin | ng value on or prior | to fezolinetant day | y 1 (inclusive) |
| Week 2 | Day 15 | 2 to 22 | | | |
| Week 4 | Day 29 | 23 to 43 | 2 to 43 | 2 to 57 | |
| Week 8 | Day 57 | 44 to 71 | 44 to 71 | | |
| Week 12* | Day 85 | 72 to 92 | 72 to 99 | 58 to 99 | 2 to 127 |
| Week 14 | D99 | 93 to 106 | | | |
| Week 16 | D113 | 100 to 127 | 100 to 127 | 100 to 127 | |
| Week 20 | D141 | 128 to 155 | 128 to 155 | 128 to 155 | |
| Week 24 | D169 | 156 to 183 | 156 to 183 | 156 to 183 | 128 to 267 |
| Week 28 | D197 | 184 to 211 | 184 to 211 | 184 to 211 | |
| Week 32 | D225 | 212 to 239 | 212 to 239 | 212 to 239 | |
| Week 36 | D253 | 240 to 267 | 240 to 267 | 240 to 267 | |
| Week 40 | D281 | 268 to 295 | 268 to 295 | 268 to 295 | |
| Week 44 | D309 | 296 to 323 | 296 to 323 | 296 to 323 | |
| Week 48 | D337 | 324 to 351 | 324 to 351 | 324 to 351 | |
| Week 52** | D365 | 352 to 376 | 352 to 376 | 352 to 376 | 268 to 376 |
| Week 55 | D386 | Last non-missin | ng follow-up day | | |

The data summary by visits will be done following the analysis windows specified in the table below:

a) Apply to liver biochemistry and INR testing

- b) Apply to complete Clinical laboratory and urinalysis, Vital signs
- c) Apply to Blood PD/PK sample, including hormones (PD only at Week 55)
- d) C-SSRS

*The analysis window for the Week 12 ECG assessment (Target Day 85) is FDay 2 through FDay 99

**The analysis window for the Week 52 ECG is last non-missing day from FDay 100 to FUD1; The analysis window for the Week 52 bone marker is FDay 2 to FUD1; The analysis window for the Week 52 TVU and biopsy assessments is FDay 2 until last treatment + 30 days.

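### The 52-week QTc threshold table is by visit only, so the plan cannot say how many women ever exceeded 450, 480 or 500 msec on fezolinetant

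*SAP*

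**What the plan says.** Section 6.5.4 of the 52-week SAP sets out the QTc category analysis in one sentence: "The QTc interval will be summarized using frequency tables for each analysis visit for values of clinical importance using the range criteria below". Below a normal row (up to and including 450 msec) come three raised rows: "Borderline | > 450", "Prolonged | > 480" and "Clinically significant | > 500".

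The ECG visits are defined in the footnotes of section 6.10.1.2. For Week 12: "The analysis window for the Week 12 ECG assessment (Target Day 85) is FDay 2 through FDay 99". For Week 52: "The analysis window for the Week 52 ECG is last non-missing day from FDay 100 to FUD1". When a window holds several records, the one closest to the scheduled day is used. For safety data a tie goes to the later record. Records from the same day are averaged if continuous. Section 6.5 cuts safety data other than adverse events and follow-up visit data at one day after the last dose.

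For liver tests, section 6.5.2.1 uses a different unit: "The subject's highest value during the entire active-dose study period". Section 6.5.2 likewise builds its hematology and biochemistry shifts from baseline to the worst finding on treatment. Section 7.1 records that version 2.0 dropped the summary of QTc change-from-baseline outliers.

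**The concern.** For rare threshold exceedances, the natural safety question is how many women ever crossed the limit while on drug. A by-visit table answers a different question: how many were above the limit at the record chosen for that visit. Two visit counts cannot be combined into a count of women, because the table does not show whether they are the same women. Nor can the table show an exceedance on an ECG that lost out to another record in its window.

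At stake is what the 52-week report can conclude about QTc. That report is descriptive, covers follow-up that is uncontrolled after Week 12, and no longer has the change-from-baseline outlier summary. The by-visit threshold table is the only categorical QTc analysis left.

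**Working it through.** The ECG section gives no rate, sample size or expected count, so there is no figure to reproduce. The check applies the SAP's own rules.

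**Inputs**
- Scheduled ECGs (protocol Table 1): screening, Day 1, Week 12, and Week 52/EOT/ED. None is scheduled between Weeks 12 and 52. Unscheduled visits are allowed (Table 1, footnote c).
- Visit window: ±3 days, so the Week 12 ECG falls on FD82 to FD88 for women randomized to fezolinetant.
- ECG windows, selection and tie rules, and cut-off: 52-week SAP 6.5, 6.10.1.1 and 6.10.1.2.
- Safety baseline (52-week SAP section 5): last value on or before the first fezolinetant dose.

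**1. Coverage.** FD2–FD99 and FD100–FUD1 meet without a gap, since 99 + 1 = 100. Every on-treatment ECG from FD2 therefore falls in a window, and one is left out only when another record there is selected. At most two records per woman reach the table.

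**2. Unscheduled ECGs.** With a Week 12 ECG on FD85 (distance 0), no ECG on another day in FD2–FD99 can be selected. With an end-of-treatment ECG present by FUD1, no earlier ECG from FD100 onward is selected, because the last one is taken. An invented example: ECGs on FD40, FD85, FD200 (505 msec) and FD365 put only FD85 and FD365 in the table.

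**3. Early-discontinuation (ED) ECGs.** Let the Week 12 ECG be on day d and a later on-treatment ED ECG on day e ≤ 99. The ED record is dropped when |e − 85| > |d − 85|; a tie goes to the later record.

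| Week 12 ECG (d) | ED ECG dropped if on | Possible days |
|---|---|---|
| FD82 | FD89–FD99 | 11 |
| FD83 | FD88–FD99 | 12 |
| FD84 | FD87–FD99 | 13 |
| FD85 | FD86–FD99 | 14 |
| FD86 | FD87–FD99 | 13 |
| FD87 | FD88–FD99 | 12 |
| FD88 | FD89–FD99 | 11 |

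An ED ECG from FD100 to FUD1 is selected if it is the last record. One up to FD99 is selected if no other record in the window is closer. One taken after FUD1 is outside the cut-off, and a maximum with the same cut-off would not recover it.

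**4. Placebo-to-fezolinetant women.** Their Week 12 ECG is the safety baseline. If the extension starts on study Day 85, study Day 365 is FD 365 − 85 + 1 = 281. They have one scheduled post-baseline ECG, and their Week 12 cell is empty unless they have an unscheduled or ED ECG by FD99.

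**5. What two visit counts can tell us.** With a and b women above a limit at the two visits and nothing displaced:

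max(a, b) ≤ women ever above the limit ≤ a + b

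The documents give no QTc rate, so the figures below are assumptions: 150 women (the planned arm size), both ECGs done, and the same rate p at each visit. Then a = b = 150p.

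| Assumed p | At each visit | Ever above (range) |
|---|---|---|
| 0.5% | 0.75 | 0.75 to 1.5 |
| 1% | 1.5 | 1.5 to 3 |
| 2% | 3 | 3 to 6 |
| 5% | 7.5 | 7.5 to 15 |

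Under these assumptions the upper limit is twice the lower. Displaced exceedances would add to it.

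**6. Rows.** A QTc of 460 meets only the > 450 row; 490 meets > 450 and > 480; 510 meets all three. The overlap repeats a woman across rows and removes none.

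**The case against.** The best defence is proportionality. The protocol names liver injury as an important potential risk and gives it stopping rules. QTc is neither an adverse event of special interest nor a discontinuation criterion, and section 1.4.2 reports no clinically meaningful ECG changes in phase 2b. The sponsor removed the QTc change outliers deliberately, on the ground that they add little medically relevant information. This stands as a reason to rate the point as modest. It does not supply the missing count, and the worst-value approach is not reserved for liver: routine hematology and biochemistry shifts use it too.

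A second defence is that other outputs cover part of the ground. Section 6.5.4 tabulates centrally read abnormal ECGs and changes from normal at baseline to abnormal. Protocol 7.5.5 lists all ECG interpretations. Protocol 5.5.1.1 makes ECG findings that the investigator judges clinically significant reportable as adverse events. This also stands in part. The abnormality tables are by visit and not by QTc limit, and neither a listing nor an adverse event table counts women by QTc threshold.

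A reader might infer that prolongation on interim ECGs is never counted. The documents do not support that. No interim ECG is scheduled, the windows have no gap, and an unscheduled ECG counts whenever it is the selected record.

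A reader might also infer that the overlapping rows lose women, or breach section 6.1, where "the percentages for the non-missing categories will add up to 100"%. Overlap loses no one. The liver table in the same SAP uses the same cumulative style, and section 6.1 leaves table formats to specifications that are not part of these documents. Only a labelling question remains.

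**Conclusion.** The point holds in a limited form. As planned, the 52-week report cannot state the number of women with any on-treatment QTc above 450, 480 or 500 msec. That follows from the SAP's rules alone and needs no assumption about displaced ECGs. In addition, the threshold table omits unscheduled ECGs when another record in the window is selected. It also omits ED ECGs over a band of 11 to 14 possible days up to FD99, in women randomized to fezolinetant who have a Week 12 ECG nearer Day 85.

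The number of omitted ECGs is not given, so the documents do not show that the report would understate QTc prolongation, only that it could. The ranges by assumed rate show scale and are not estimates. No power, alpha or efficacy result is affected. This is an inexpensive improvement to a descriptive safety summary.

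**What to change.** In section 6.5.4 of the 52-week SAP, add one table: number and percentage of women by maximum post-baseline on-treatment QTc, against baseline QTc category. Include all scheduled, unscheduled and early-discontinuation ECGs after the first fezolinetant dose (from FD2 in the SAP's windows) up to one day after the last dose. State whether same-day records are averaged first, as the existing rule does. Section 6.5.2.1 is the precedent for the highest-value rule.

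Separately, state whether the QTc rows are cumulative or exclusive. If exclusive, they read ≤ 450, > 450 to 480, > 480 to 500 and > 500 msec. Apply the same choice to the by-visit table, which stays.

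Align section 6.5.4 of the 12-week SAP, which has the same rows and a by-visit layout.

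The cost is SAP wording and one extra table per report, with no new ECGs. The drawback is that women with more ECGs have more chances to exceed a limit. A footnote should say so and note that placebo-to-fezolinetant women have one scheduled post-baseline ECG, whereas those on fezolinetant throughout have two.

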6.5.5 Other Safety-Related Assessments

C-SSRS results will be summarized by treatment group and analysis visit based on SAF_F.

Ultrasound results (endometrial thickness) and bone marker results will be summarized for the SAF_F population using mean, standard deviation, minimum, maximum and median by treatment group and visit. The within-subject change will be calculated per visit as the post-baseline measurement minus the baseline measurement and summarized by treatment group and visit. The listing will be based on the complete SAF population, including all placebo data and subjects randomized to placebo who never received fezolinetant, because these data were not included in the double-blind 12-week analysis.

Baseline biopsy will be defined as the non-missing value on or prior to first dose of study drug. Biopsy results will be listed based on the complete SAF population, including all placebo data and subjects randomized to placebo who never received fezolinetant, because biopsy data was not included in the double-blind 12-week analysis. Post-baseline biopsy results for subjects originally randomized to placebo will still be listed.

6.6 Analysis of Pharmacokinetics

The statistical methods for PK data will be described in a separate analysis plan. Results of the population PK analysis will not be reported in the Clinical Study Report but in a separate population PK report.

Plasma concentration of fezolinetant and ES259564 will be listed.

6.6.1 Estimation of Pharmacokinetic Parameters

All details of the population PK analysis will be described in a separate analysis plan.

6.7 Analysis of Pharmacodynamics

Serum concentrations of sex hormones (LH, FSH, E2, Testosterone Total/Free, Androstenedione, DHEA, Estrone) and SHBG will be summarized using descriptive statistics (number of subjects, mean, SD, median, minimum and maximum) for each analysis and for change from the baseline to each postdose visit, if the data is available.

6.8 Other Analyses

Not applicable.

6.9 Interim Analysis (and Early Discontinuation of the Clinical Study)

There will be no interim analysis.

6.10 Additional Conventions

In case of data issues or findings pertaining to the 12-week period after the 12-week lock and before the final lock, an errata form will be issued to document those data discrepancies.

6.10.1 Analysis Windows

Study Day for analysis windows during the double-blind treatment phase will be calculated as date of visit/assessment – first dose date +1.

Study Day during the extension phase will be calculated as date of visit/assessment – first dose date of the extension phase +1.

Study Day for the follow-up (FUD) phase will be calculated as date of visit/assessment – last dose date of study treatment (Date of EOT).

Fezolinetant Study Day (FD) will be calculated as date of visit/assessment – first dose date of fezolinetant +1. Note that this is the same as Study Day for subjects randomized to fezolinetant in the double-blind treatment phase. Post-baseline data prior to first dose of fezolinetant Day 1 is excluded from the analyses described in this SAP unless otherwise noted.

6.10.1.1 Efficacy Analysis Windows

For the analysis windows, the last day is always the last day of exposure to overall study treatment. For VMS diary data the last day of exposure includes events reported until

8:00AM the following day. For example, the Week 1 average will include diary data from 8AM on Day 1 through 7:59AM on Day 8.

For both VMS and non-VMS efficacy, the end of overall treatment is defined as the last day of treatment (e.g., discontinued study or entered follow-up period) and the follow-up period begins at last overall treatment + 1 day.

| Analysis study week | Analysis window |
|---------------------|--|
| Baseline | Non-missing days from D-10 up to and including D-1 |
| Week 1 | FD1 to FD7 |
| Week 2 | FD8 to FD14 |
| Week 3 | FD15 to FD21 |
| Week 4 | FD22 to FD28 |
| Week 5 | FD29 to FD35 |
| Week 6 | FD36 to FD42 |
| Week 7 | FD43 to FD49 |
| Week 8 | FD50 to FD56 |
| Week 9 | FD57 to FD63 |
| Week 10 | FD64 to FD70 |
| Week 11 | FD71 to FD77 |
| Week 12 | FD78 to FD84 |
| Week 16 | FD110 to FD116 |
| Week 20 | FD138 to FD144 |
| Week 24 | FD166 to FD172 |
| Week 28 | FD194 to FD200 |
| Week 32 | FD222 to FD228 |
| Week 36 | FD250 to FD256 |
| Week 40 | FD278 to FD284 |
| Week 44 | FD306 to FD312 |
| Week 48 | FD334 to FD340 |
| Week 52 | FD362 to FD368 |
| Week 53 (Follow-up) | FUD1 to FUD7 |
| Week 54 (Follow-up) | FUD8 to FUD14 |
| Week 55 (Follow-up) | FUD15 to FUD21 |

The study week determination for the vasomotor symptoms data is based on the following:

Calculations for weeks up through Week 12 end on the last day of the study week. Calculations for weeks beyond the double-blind treatment period are centered about protocol-specified visits to match visit-based efficacy assessments. For example, the Week 12 analysis window ends on FD84 (7*12=84), but the Week 16 visit is centered around protocol specified FD113 (FD110 to FD116). Calculations in the follow-up period end on the last day of the study week, based on study days in the follow-up period.

Weeks 44, 48 and 52 will be missing for subjects randomized to placebo during the doubleblind treatment period because they are only on active treatment for 40 weeks.

A weekly average will be calculated if any information, including zero VMS events, was reported for 4 or more days.

All other efficacy assessments, including those from unscheduled visits and regardless of visit label, will be allocated to analysis visits based on the table below:

| Target day | Analysis window | Analysis visit |
|------------|---|----------------|
| D1 | last non-missing value on or prior to day 1 | Baseline |
| D29 | FD22 to FD36 | Week 4 |
| D85 | FD72 to FD 92 | Week 12 |
| D113 | FD106 to FD120 | Week 16 |
| D141 | FD134 to FD148 | Week 20 |
| D169 | FD162 to FD176 | Week 24 |
| D197 | FD190 to FD204 | Week 28 |
| D225 | FD218 to FD232 | Week 32 |
| D253 | FD246 to FD 260 | Week 36 |
| D281 | FD274 to FD288 | Week 40 |
| D309 | FD302 to FD316 | Week 44 |
| D337 | FD330 to FD344 | Week 48 |
| D365 | FD358 to FD372 | Week 52 |

The VMS efficacy windows are smaller because they are calculated from daily data and are not dependent on the scheduling of visits. The non-VMS efficacy endpoint are not collected during the follow-up period.

If more than one observation exists within the analysis window, the observation closest to the scheduled visit day will be selected for that visit. If there are two observations that have the same distance from the scheduled day, the value that is before the scheduled day will be selected in the analysis. If more than one observation is made on the same day, an average value if continuous, or the worst value if categorical, will be included in the analysis.

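### 52-week SAP: the closing diary window is centred on the final visit but cut at the last dose, so whether the final VMS average exists depends on visit timing

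*SAP*

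**What the plan says.** Four rules in the 52-week SAP, Section 6.10.1.1, act together on the VMS diary.

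- Position: "Calculations for weeks beyond the double-blind treatment period are centered about protocol-specified visits to match visit-based efficacy assessments". This gives "FD362 to FD368" for Week 52 and "FD278 to FD284" for Week 40.
- Cut: "For the analysis windows, the last day is always the last day of exposure to overall study treatment". Follow-up starts the next day, and its first seven days form Week 53.
- Minimum: "A weekly average will be calculated if any information, including zero VMS events, was reported for 4 or more days".
- Switch groups: women first randomized to placebo have no Week 44, 48 or 52 value "because they are only on active treatment for 40 weeks", so Week 40 is their closing time point.

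Section 6.10.1 counts the fezolinetant day (FD) as assessment date minus "first dose date of fezolinetant +1". In the switch groups FD1 is therefore the first extension dose.

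Section 6.10.1.1 explains the diary windows this way: "The VMS efficacy windows are smaller because they are calculated from daily data and are not dependent on the scheduling of visits".

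Protocol Table 1 puts Visit 5 on Day 85 and Visit 15 on Day 365, each within 3 days either way.

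**The concern.** At every earlier extension week, a woman still on treatment has all seven window days on drug. Only the closing window straddles the end of treatment. If it is cut at the last dose, it keeps the days up to about its midpoint, which is also about where the 4-day minimum falls. A shift of one day in the final visit, well within the protocol's allowance, then decides whether the average exists.

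The 52-week SAP sets out to describe efficacy for up to 52 weeks of exposure (Section 2.1). Followed as written, it can leave the last on-treatment frequency and severity missing for women who finished treatment and kept their diaries. The number of women behind that row would then reflect visit scheduling.

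**Working it through.** **Inputs.** Windows, cut, minimum and FD definition: 52-week SAP 6.10.1 and 6.10.1.1. Visit days and the 3-day allowance: Protocol Table 1 and footnote c.

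**Reproducing the SAP's windows.** (7w + 1) ± 3 gives all ten rows from Week 16 to Week 52, including the SAP's worked example: w = 16 gives FD113 ± 3 = FD110 to FD116. For w = 40 it gives FD278 to FD284, and for w = 52 FD362 to FD368.

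**When is the last dose?** The documents point both ways.

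- Visit day: Week 52 questionnaires are completed before dosing (Protocol 2.2.1); Week 52 samples are predose (Table 1, footnotes q and r); the dose is taken on site on visit days (footnote v); SAP 6.10.1 equates the last dose date with the EOT date; and Day 386, described as about 3 weeks after the last dose, is 365 + 21.
- Day before: treatment lasts 52 weeks, and 52 × 7 = 364; no drug is dispensed at Visit 15.

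Both readings are carried through.

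**Formula.** Available days = min(window end, last-dose FD) − window start + 1, floored at 0.

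**Original arms, Week 52**

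| Visit 15 on Day | 362 | 363 | 364 | 365 | 366 | 367 | 368 |
|---|---|---|---|---|---|---|---|
| FD362–368, dose on visit day | 1 | 2 | 3 | 4 | 5 | 6 | 7 |
| FD362–368, dose day before | 0 | 1 | 2 | 3 | 4 | 5 | 6 |
| FD358–364, dose on visit day | 5 | 6 | 7 | 7 | 7 | 7 | 7 |
| FD358–364, dose day before | 4 | 5 | 6 | 7 | 7 | 7 | 7 |

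The documents give no visit distribution, so the share able to reach 4 days under the present window is shown by scenario (visit day / day before):

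- every visit on Day 365: 100% / 0%
- half on Day 365, the rest even over the other six days: 0.5 + 0.5 × 3/6 = 75% / 0.5 × 3/6 = 25%
- even over the seven days: 4/7 = 57% / 3/7 = 43%

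**Switch groups, Week 40.** With the first extension dose on the Visit 5 day, Visit 15 falls on FD = 281 + (Visit 15 offset − Visit 5 offset), since 365 − 85 + 1 = 281. Four days in FD278 to FD284 need a last dose on FD281 or later, so the difference in offsets must be at least 0 (visit day) or at least 1 (day before). Combinations that qualify:

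| Visit 15 | Visit day | Day before |
|---|---|---|
| Early | 6 of 21 | 3 of 21 |
| On time | 4 of 7 | 3 of 7 |
| Late | 18 of 21 | 15 of 21 |
| All | 28 of 49 | 21 of 49 |

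These are counts, not probabilities. If both visits independently follow the half-on-target pattern, P(difference = 0) = 0.25 + 6/144 = 0.292. Then P(difference ≥ 0) = (1 + 0.292)/2 = 0.646 and P(difference ≥ 1) = 0.354, or 65% / 35%.

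With FD274 to FD280, the last dose must fall on FD277 or later. That holds in 46 of 49 or 43 of 49 combinations. Under the same pattern, 1 − 3/144 = 98% and 1 − 6/144 = 96%.

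**Margin for a missed entry.** Exactly 4 available days tolerate none. Assuming independent daily completion, 0.95⁴ = 0.81 and 0.85⁴ = 0.52. The 85% figure is the protocol's retraining threshold (Section 8.1.1), so it is a low scenario. With 7 available days, the chance of at least 4 entries is above 99.9% at 95% and 98.8% at 85%.

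**The case against.** The case against rests on stakes, size and the choice of remedy.

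- **Stakes.** The affected rows are exploratory and descriptive, with no comparisons (52-week SAP 5.3 and 6.1). The Week 24 secondary endpoint is untouched. In women still on treatment, Week 48 (Week 36 in the switch groups) keeps all seven days. No direction of bias is shown. All of this stands and limits the importance of the point.
- **Data are not lost.** Days after the last dose are reported under Week 53. True, but on-treatment days that fall short of the minimum contribute to no closing average.
- **Last-dose evidence.** Several passages, including the EOT wording in SAP 6.10.1, point to a visit-day last dose, and the starkest figures need the other reading. That is fair. Yet on the visit-day reading a woman in the original arms seen early still has no value, and one seen on time has no margin.
- **Size is assumed.** The visit patterns and completion rates are scenarios, so the loss cannot be estimated from the documents. This also stands. The mechanism does not depend on them.
- **The sentence on scheduling.** It explains why diary windows are narrow, and their boundaries are indeed fixed in FD. But whether a closing average exists still follows the last dose date, and so the final visit.
- **Another remedy.** Using the last seven on-treatment days always gives seven days. It would, however, need a rule on who counts as having reached Week 52, and it would cover different treatment days in different women.

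Reading the cut as not applying does not help. With an on-time visit and a visit-day last dose, FD366 to FD368 would then be off-drug days counted in both Week 52 and Week 53.

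**Conclusion.** The concern holds. Cutting at the last dose is defensible. The fault is combining it with a window about half of which lies after the planned end of treatment, together with a 4-day minimum. In the original arms, any Visit 15 before Day 365 gives no Week 52 average on either last-dose reading. An on-time visit gives either exactly 4 days or too few. In the switch groups, 21 of 49 permitted visit combinations fail on the visit-day reading and 28 of 49 on the day-before reading, taking the first extension dose as given on the Visit 5 day.

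The likely effect is a scheduling-driven loss of n in the closing frequency and severity summaries. Its actual size is unknown without the visit dates. The Week 4 and Week 12 co-primary analyses, the alpha and, for women still on treatment, the Week 24 and Week 48 summaries are not affected. It should be fixed because the closing week is the direct evidence at the horizon this SAP sets out to describe.

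**What to change.** In the 52-week SAP, Section 6.10.1.1, set the Week 52 diary window to FD358 to FD364 and the Week 40 window to FD274 to FD280. Use Week 40 as redefined in all four groups so that they match. Apply both windows to every subject with no completer condition, and keep the cut at last exposure and the 4-day minimum. An early discontinuer then gets a value only if she was treated on at least 4 days of that fixed week.

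This is the SAP's own convention for Week 12 (FD78 to FD84). Both windows lie inside the visit-based windows for the same visits (FD358 to FD372 and FD274 to FD288). FD358 to FD364 is also the 7-day recall period of a PROMIS SD form completed on Day 365.

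Separately, the passages bearing on whether the last dose falls on Day 364 or Day 365 must be reconciled. The windows work on either reading.

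The cost is a wording change and minor programming, with no new data. The two windows move 4 days earlier and are no longer centred on the visit, including Week 40 in the continuing arms, where the present window is not at risk. A small dependence on scheduling remains in the switch groups (3 or 6 of 49 combinations).
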